JHM IRB - eForm A – Protocol

1. Abstract

Atrial fibrillation (AF) is the most common sustained cardiac arrhythmia with increasing morbidity and mortality. A catheter-based AF ablation technique that isolates pulmonary veins (PV) from the left atrium has been established to disrupt AF. Despite significant development, AF ablation with pulmonary vein isolation (PVI) is reported to have a success rate of 40-80% in various AF populations. Many factors noted in the occurrence and progression of AF namely genetic factors, clinical parameters including biomarkers, heart disease and extrinsic influences like sleep apnea, have also been noted to impose direct effect on its recurrence following an ablation procedure, whether PVI alone or with additional ablation lines. Although major developments in techniques and energy delivery systems have occurred since AF ablation was implemented a decade ago, little is known on the predictors of success or failure of the procedure.

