Moreover, it is thought that a trigger-based mechanism is responsible for initiating AF. Several studies have localized these triggers to the PV antra. This has led to the development of a PV trigger ablation, or PVI, that proved to be particularly more successful in paroxysmal AF. In fact, persistent AF appears to be more reliant upon fibroblast proliferation and myocyte-fibroblast coupling than paroxysmal AF with obvious implications on its management. Despite our knowledge that fibrotic substrate is responsible for the perpetuation of persistent AF, several ablation techniques targeting these extra-pulmonary veins sites have failed to prove an additional benefit to PVI alone. Nevertheless, two recently developed technologies, aimed at detecting AF substrate with high precision, seem to constitute a potential breakthrough in the management of persistent AF. On one hand, late gadolinium-enhanced MRI (LGE-MRI) is a well-established method to identify fibrosis in the myocardium. Recent reports from a single center have shown that MRI-based left atrial fibrosis detection is able to predict the outcome of the procedure. Hence, targeting lesions seen on LGE-MRI in the setting of persistent AF is an option yet to be explored and compared to the widely adopted, yet suboptimal, PVI. On another hand, a novel ablation method with promising results is focal impulse and rotor modulation (FIRM). Undergoing wide sampling of the atria with spatiotemporal and computational mapping while in AF has identified areas with stable organized rotational electrical activity (rotors). Several studies are under way to prove the reproducibility of rotor mapping, with more groups reporting improved rates of acute and long-term suppression of AF with ablation of FIRM-identified rotors. (Narayan et al., 2014; Shivkumar, Ellenbogen, Hummel, Miller, & Steinberg, 2012) (Akoum et al., 2015)

The SIMPle AF study will be a randomized clinical trial designed to test the hypothesis that ablation tailored to the underlying substrate using either LGE-detected dense scar or rotor anchor sites predicted by computational modeling is superior to anatomic non-tailored PVI ablation in patients with persistent AF. For the present study, we plan to enroll a total of 30 patients. Following the collection of preliminary outcome data, we plan on enlarging the study to a multicenter randomized controlled trial enrolling a total of 300 patients, with the support of an NIH grant.

2. Objectives

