The main objective of the study is to identify the optimal ablation strategy for suppression of persistent AF.

The secondary objectives of the study are:

- To define the local myocardial image characteristics of slow conduction AF substrates.
- To define the local myocardial structural changes post ablation that associate with AF suppression at 1-year follow-up
- To compare cardiac remodeling and atrial function at 1-year follow-up between PVI only and tailored catheter ablation groups

3. Background

Atrial fibrillation (AF) is associated with increased risk for mortality, heart failure, and thromboembolic events, and has a worldwide prevalence of >33.5 million (Benjamin et al., 1998; Chugh et al., 2014; Estes et al., 2011; Schnabel et al., 2015). Catheter ablation of AF is evolving as an effective therapy for symptomatic AF (Calkins et al., 2012). Recurrent AF after ablation, however, remains a problem and has been reported to associate with the baseline extent of left atrial (LA) late gadolinium enhancement (LGE) on cardiac magnetic resonance (CMR) (Marrouche et al., 2014; McGann et al., 2014). Mechanistically, persistent AF appears to be more reliant upon fibroblast proliferation and myocyte-fibroblast coupling than paroxysmal AF, which is primarily dependent upon pulmonary vein triggers (Haissaguerre et al., 1998; Inoue et al., 2012; Wilber, 2012). Therefore, we hypothesize that the substrate for persistent AF is detectable on atrial LGE-CMR and variable among patients, and that the substrate predicts patient outcomes after anatomic non-tailored ablation, and is more likely to respond to individually tailored ablation approaches. Two individually tailored approaches will be studied including empiric targeting of dense LGE, confirmed on bipolar mapping to have voltage <0.1 mV, and modeling based targeting of rotor anchor sites.

4. Study Procedures

a. Study Design

Initially, we propose prospective enrollment of 30 participants with persistent AF. Patients presenting to our institution who meet the inclusion criteria will be asked to participate in the study. All patients will undergo routine clinical care including echocardiography as indicated.

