All patients will undergo a LGE-MRI within 30 days prior to the ablation procedure. The clinical purpose of the initial MRI is to define the anatomy of the heart chambers as well as the vessels for procedure planning. For research purposes, we will use this initial clinical MRI to delineate atrial structural remodeling or fibrosis to be used during the procedure in patients randomized to group 2 (pulmonary vein isolation + scar-based ablation) and for later analysis in all patients.

Imaging is done at our institution and will be reviewed for quality by the study staff. LGE-MRI sequences that do not meet quality standards for fibrosis analysis will not be further processed and these patients will be excluded from the study. Subjects for whom images are successfully evaluated will be randomized to the study groups.

This will be followed by block randomization in 1:1:1 format to a) pulmonary vein isolation (PVI) only (current standard of care), b) PVI plus targeting of dense LGE sites, which are confirmed on bipolar mapping to have voltage <0.1 mV, and c) PVI plus targeting of rotor anchor sites predicted by modeling.

At baseline, all patients will be evaluated for their quality of life (QOL) using the Short-form health survey (SF-36) (Ware & Sherbourne, 1992) for overall as well as AF-related impact on quality of life (Refer to additional study documents). The severity of symptoms will be tested using the European Heart Rhythm Association (EHRA) score of atrial fibrillation and the Canadian Cardiovascular Society (the CCS-SAF) scale (Dorian et al., 2006). Clinical data will be stored electronically and linked to a specific research ID number. Information linking de-identified data to the patients will be stored in the locked research office, in a password-protected file. Only members of the research team, in charge of collecting clinical information, will have access to this file. Individual subject binders containing signed consent forms and clinical source documentation will be labeled using study subject numbers and stored in the locked research office mentioned previously.

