Patients undergoing MRI angiogram are routinely injected with gadolinium as contrast. Gadolinium-based MRI contrast agents are used to visualize scar/ablation lesions in the atrial wall (McGann et al., 2014). Gadolinium chelates used as intravenous contrast media are extremely safe in patients with normal kidney function and do not exhibit the nephrotoxicity associated with iodinated media. Minor reactions including nausea and hives may occur in a small percentage of cases. Severe anaphylactic reactions are extremely uncommon (Runge, 2001).

- b. Justification and safety information if FDA approved drugs will be administered for non-FDA approved indications or if doses or routes of administration or participant populations are changed.

Gadolinium (total dose of 0.2 mmol/kg) will be administered 10 minutes prior to delayed enhancement imaging to evaluate for the presence of myocardial scar. Gadolinium-based contrast agents are not FDA-approved for diagnosis of cardiac disease by MRI. However, these agents have been routinely used for more than 10 years at the JHH and other centers for clinical and research purposes to evaluate diseases of the myocardium and vessels (Akoum & Marrouche, 2014) (Zareian et al., 2015). The standard gadolinium dose at JHH and other institutions in cardiac MRIs is a maximum of 0.2 mmol/kg.

- c. Justification and safety information if non-FDA approved drugs without an IND will be administered. N/A

7. Study Statistics

- a. Primary outcome variable.

Data from AliveCor® Mobile ECG rhythm device recordings, follow-up visits (examinations and ECGs), and QOL/follow-up questionnaires will be used to identify the success rates of the procedure. Procedure failure is defined as symptomatic or asymptomatic AF/Atrial flutter/Atrial tachycardia of at least 30 seconds duration that is documented by an ECG or device recording system, occurring after the 3-month blanking period following catheter ablation. Individually tailored ablation strategies for suppression of persistent AF have not been investigated. We hypothesize that individually tailored ablation strategies will improve AF/AT suppression compared to PVI alone. The association of time to AF/AT recurrence with ablation strategy will be examined in 30 randomized patients.

- b. Secondary outcome variables.

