During ablation, the spatial coordinates and electrogram characteristics of >200 intra-cardiac points are sequentially sampled and saved. We hypothesize that sites with slow conduction during sinus rhythm,

representing AF substrates, are detectable as sectors with intermediate LGE intensity [image intensity ratio (IIR) 0.9-1.6] on LGE-CMR. We will co-register the spatial coordinates of sites exhibiting slow conduction with pre-procedural LGE-CMR for 30 patients. We will then compare the baseline image intensity ratio of sites with slow conduction versus other sites.

Catheter ablation results in long-term AF suppression in approximately 50% of patients with persistent AF. We hypothesize that AF suppression at 1-year will be associated with the presence of IIR>1.6 at the 1-year LGE-CMR in sectors where slow conduction was observed at baseline. We will co-register the baseline spatial coordinates of sites exhibiting slow conduction with 1-year post-procedural LGE-CMR images for 30 patients randomized to ablation. We will then compare the 1-year image characteristics of sectors with slow conduction among patients with and without AF suppression at 1-year follow-up.

Catheter ablation promotes scar formation and more extensive ablation strategies may adversely affect left atrial function. However, AF recurrences and continuation of antiarrhythmic drug therapy may also lead to progression of atrial and ventricular dysfunction. We hypothesize that more extensive patient tailored approaches will have less negative impact on atrial and overall cardiac function. We will measure the change (baseline to 1-year MRI) in left atrial and left ventricular regional and global strain in 30 randomized patients. We will then examine the association of the change in regional and global strain with ablation strategy.

- c. Statistical plan including sample size justification and interim data analysis.

Based on the variable success rate of 40-80% in AF ablation, we anticipate that the study cohort of 30 patients would produce adequate sample size in all treatment arms and be sufficient to make meaningful statistical comparison.

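### Section 7c calls 30 patients sufficient to compare the arms, but power is at most about 65% even if the whole cited 40-80% range is taken as the treatment effect

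*Combined protocol and SAP*

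**What the plan says.** Section 7c holds the protocol's only sample-size justification. From the spread in reported ablation success it concludes that the study "cohort of 30 patients would produce adequate sample size in all treatment arms and be sufficient to make meaningful statistical comparison". It states no difference to detect, power, expected number of recurrences or dropout allowance.

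Section 1 shows where the range comes from: PVI is "reported to have a success rate of 40-80% in various AF populations". Section 7b gives a figure for the population actually under study: "Catheter ablation results in long-term AF suppression in approximately 50% of patients with persistent AF".

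On allocation, section 4a says "This will be followed by block randomization in 1:1:1 format", so each of the three arms has 10 patients. Section 7c plans the Pearson chi-square test for group differences and the log-rank test for the Kaplan-Meier curves, two-tailed, with a 0.05 threshold and no multiplicity rule.

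On purpose, section 1 describes a "randomized clinical trial designed to test the hypothesis that ablation tailored to the underlying substrate" (by dense scar or by modelled rotor sites) "is superior to anatomic non-tailored PVI ablation in patients with persistent AF". Section 7a adds: "We hypothesize that individually tailored ablation strategies will improve AF/AT suppression compared to PVI alone". A secondary objective in section 2 compares remodelling "between PVI only and tailored catheter ablation groups". Nowhere is the primary contrast fixed as pairwise, three-arm or pooled.

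Sections 1 and 11 also present the 30 patients as a source of preliminary data before a planned 300-patient multicentre trial. Section 7c does not repeat that qualification.

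**The concern.** A spread of success rates across AF populations says nothing about the difference between arms that 10 patients per arm could detect. Yet 7c moves directly from that spread to a claim of sufficiency in every arm, next to a superiority hypothesis and a significance rule.

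Section 7c is where a reader looks to judge what a result can mean. Someone told that the sample is sufficient could take a non-significant result as evidence that tailored ablation adds nothing. The same data are meant to support the application for the larger trial.

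**Working it through.** **The plan's own figure.** There is none to reproduce. Section 7c states neither power nor an effect, so the check asks what power the stated design has.

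**Inputs from the protocol.** 30 randomized patients (7a); 1:1:1 allocation (4a), so 10 per arm, or 20 vs 10 with the tailored arms pooled; two-sided 0.05 with Pearson and log-rank tests (7c); 40-80% (1, 7c); about 50% in persistent AF (7b).

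**Assumptions.** The protocol gives no effect, so two are tried. The first, 40% vs 80%, uses the whole cited range and is deliberately generous. The second, 50% vs 80%, starts from the persistent-AF figure. Both assume no dropout and no multiplicity correction. The log-rank figures assume exponential recurrence.

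**Pearson power, by exact enumeration.** For success counts a of n1 and b of n2, with t = a + b and N = n1 + n2:

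- X² = N[a(n2 − b) − b(n1 − a)]² / [n1 n2 t (N − t)], significant if the 1-df p-value is below 0.05.
- Power is the sum of Bin(a; n1, p1) × Bin(b; n2, p2) over all significant (a, b).
- For three arms, X² = Σ(k − 10p̂)² / [10p̂(1 − p̂)] on 2 df, where k is the success count in each arm and p̂ the overall success proportion.

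**Log-rank power, by simulation.** Each arm has exponential recurrence times set to give its 1-year success p, so the hazard ratio is ln(p2)/ln(p1): ln 0.8/ln 0.4 = 0.244, or ln 0.8/ln 0.5 = 0.322. Repeated runs of 4,000 to 8,000 trials agreed to within 1-2 points.

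| Contrast (both tailored arms effective) | 40% vs 80%: Pearson to log-rank | 50% vs 80%: Pearson to log-rank |
|---|---|---|
| One tailored arm vs PVI (10 vs 10) | 42-47% | 25-30% |
| Three-arm test (2 df) | 47-52% | 29-34% |
| Pooled tailored vs PVI (20 vs 10) | 61-65% | 41-44% |

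The normal approximation for the first cell agrees: [√10 × 0.4 − 1.96 × √(2 × 0.6 × 0.4)] / √(0.24 + 0.16) = (1.265 − 1.358)/0.632 = −0.147, which gives 44%.

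**Chance of missing the benefit (100% minus power).** At 40% vs 80%: 53-58% pairwise, 48-53% three-arm, 35-39% pooled. At 50% vs 80%: 70-75%, 66-71%, 56-59%.

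**If only one tailored arm works.** Pooled Pearson power falls to 18% (40% vs 80%) or 13% (50% vs 80%). Three-arm power is about 43% or 25-26%.

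**With an assumed 10% dropout (log-rank).** 45%, 51% and 63% at 40% vs 80%; 28%, 31% and 42% at 50% vs 80% (pairwise, three-arm, pooled).

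**Events.** Expected recurrences in all 30 patients: 6 + 2 + 2 = 10 at 40/80/80, or 5 + 2 + 2 = 9 at 50/80/80.

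**Observed results at exactly the assumed rates.**

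- 4/10 vs 8/10: X² = 20(4 × 2 − 8 × 6)²/(10 × 10 × 12 × 8) = 3.33, p = 0.068.
- Three arms at 4, 8 and 8 of 10: X² = 4.80 on 2 df, p = 0.091.
- 4/10 vs 16/20: X² = 4.80 on 1 df, p = 0.028.
- 5/10 vs 16/20: X² = 2.86, p = 0.091. As three arms (5, 8, 8): p = 0.24.

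**Precision.** The 95% CI half-width for a difference in 1-year success is 1.96√[p1(1 − p1)/10 + p2(1 − p2)/n2]. Pairwise, 40% vs 80% gives 1.96√(0.024 + 0.016) = 39 points, and 50% vs 50% gives 1.96√(0.025 + 0.025) = 44 points. Pooled (n2 = 20), the range is 35-38 points.

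**For scale.** Pearson power of 80% would need 23 (pairwise), 20 (three-arm) or 16 (pooled) per arm at 40% vs 80%, and 39, 35 or 28 at 50% vs 80%.

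**The case against.** The strongest reply is that this is a pilot. Sections 1 and 11 say that the 30 patients supply preliminary data for a 300-patient trial, section 4a describes them as an initial enrolment, and a pilot need not be powered. That stands as a defence of choosing 30. It does not defend 7c, which claims sufficiency for comparison and does not mention the pilot role. The two statements conflict.

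Second, no stated figure is wrong. The plan sets no 80% target and never offers 40% vs 80% as an effect, and the 50% in 7b refers to catheter ablation in persistent AF generally, not to the PVI-only arm. All of this is correct. The fault is an unsupported claim, not a slip in a calculation, and both effect sizes are assumptions. But the first is as generous as the cited range allows, and the claim still fails.

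Third, the hypothesis sets tailored ablation as a group against PVI, which fits the pooled contrast best, and that is where the figures are least damaging: 61-65% power, and 4/10 vs 16/20 would be significant. This is fair, but even this most favourable case misses the assumed benefit about one time in three. It also depends on both tailored arms working.

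Finally, the superiority wording in section 1 can be read as describing the whole programme, since the next sentence separates out the present 30 patients. That reading is possible, so the change there is clarifying, not essential.

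**Conclusion.** The concern holds. The adequacy statement in 7c is not supported by its stated basis and is contradicted by the design's actual power: no more than about 65% under the most favourable contrast and a generous effect, and 25-44% when the comparison starts from the protocol's persistent-AF rate. These figures assume full follow-up, no multiplicity correction and, for the upper ends, exponential recurrence. Other formulas move them without changing the conclusion. At 40% vs 80%, for example, pairwise power is 51.5% by Schoenfeld's formula and 25.3% with Fisher's exact test; pooled, the same two give 55.8% and 53.7%.

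The preliminary-stage wording elsewhere reduces the risk of misreading but does not make the sentence true. Nothing here argues against enrolling 30 patients.

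**What to change.** **Section 7c (essential).** Delete the adequacy sentence and put in its place:

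> These 30 patients (10 per arm) are the preliminary stage described in section 1. At two-sided 0.05, with no dropout and no multiplicity correction, power for 1-year success of 40% on PVI vs 80% in each tailored arm is about 42-47% for one tailored arm vs PVI, 47-52% for the three-arm test and 61-65% for pooled tailored arms vs PVI. For 50% vs 80% it is about 25-30%, 29-34% and 41-44% (lower figure Pearson, upper figure log-rank with exponential recurrence assumed). The 95% CI half-width for a pairwise difference in 1-year success is about 39-44 percentage points. Between-arm comparisons are exploratory and are reported as estimates with 95% CIs (hazard ratio or Kaplan-Meier difference for time to recurrence). A non-significant result is not evidence of no benefit.

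If the team prefers not to put assumption-dependent power figures in the protocol, the preliminary aim, the CI width and the last two sentences would be enough to remove the false claim.

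**Section 7c, after the significance threshold.** Add:

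> For between-arm comparisons in these 30 patients, p < 0.05 is nominal and does not establish superiority.

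**Section 1 (clarifying).** Reword the superiority sentence so that the 30-patient stage gives preliminary estimates and the planned 300-patient trial tests the hypothesis.

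**Cost.** Wording in three places. No patients are added and no planned test changes; Cox hazard ratios and Kaplan-Meier curves are already in the plan. The price is a less favourable statement of adequacy, and the 30-patient comparison can no longer be presented as a test of superiority.

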A pre-ablation cardiac MRI is clinically indicated to assess baseline cardiac anatomy prior to procedure. Routine and LGE protocols will be used to acquire MR images. All patients will be asked to undergo a repeat LGE-MRI 12 months after the ablation. This is done for research purposes. Renal function is routinely monitored prior to gadolinium-enhanced MRI as a standard of clinical care.

With regards to the ablation procedure, all patients will undergo AF ablation. The procedure consists of circumferential pulmonary vein lesions under electro-anatomical guidance using CARTO (Biosense Webster Inc., Diamond Bar, CA). Operators will use either a 3.5mm irrigated tip radiofrequency ablation catheter (ThermoCool SmartTouch, Biosense Webster Inc., Diamond Bar, CA) or a cryoballoon catheter (Arctic Front Advance, Medtronic Inc., Minneapolis, MN). This procedure is FDA approved and will be conducted in all treatment arms according to standard of care. However, patients in the second group will undergo additional targeting of dense LGE sites, confirmed on bipolar mapping to have voltage <0.1 mV and patients in the third group will undergo targeting of rotor anchor sites as predicted by computational modeling. A detailed protocol of rotor ablation is described in the literature and shows no added complications compared to the conventional procedure (Narayan et al., 2014).

To prevent short-term recurrence of AF, patients will be kept on anti-arrhythmic regimen for the first 1 to 3 months after the ablation to be discontinued thereafter in the absence of AF recurrence, at the discretion of the treating physician. In addition, standard protocols for anticoagulation prior to, during, and after the ablation procedure will be applied.

After the ablation, clinical follow-up visits are scheduled at 3, 6 and 12 months. Research follow-up questionnaires and 12-lead ECG recordings will be done at the same day of the visits. All patients will undergo rhythm monitoring to detect AF recurrence using a portable, smartphone operated, AliveCor® Mobile ECG device. The AliveCor® Mobile ECG is a mobile, clinical-quality electrocardiogram (ECG) recorder. The software application can store thousands of recordings on smartphones or tablets and these recordings are wirelessly transmitted to AliveCor, Inc. (AliveCor) servers accessible to authorized users including healthcare providers. This device will be provided to the patients at no cost after enrollment in the study.

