Prior to ablation, patients will be asked to complete 7 days of twice-daily 1-minute rhythm monitoring using the AliveCor® device. After the procedure, follow-up will be done on a weekly basis through trans-telephonic transmissions of ECG recordings. Periodic reminders will be sent to patients (via telephone, email, or mail) regarding follow up transmissions in the event that a weekly transmission is missed. Although preferred, it is not imperative that all patients complete all weekly follow up transmissions. In addition, study participants will be advised to provide recordings if they experience heart-related symptoms (palpitations, shortness of breath, rapid heartbeat, chest pain). This extensive rhythm monitoring protocol is not standard of care and is done for research purposes. Review of the rhythm monitoring data will be performed in accordance with current clinical guidelines. The device software and the investigators will analyze rhythm strips and a report will be available to the research team and to the treating physician upon his/her request.

In addition, upon detection of any arrhythmia with important clinical implications, the investigators will notify the electrophysiologist involved in the care of the patient. The research team may contact the patient directly if prompt action is advised, such as reporting to the local emergency room or following up with their electrophysiologist. The rhythm monitoring protocol utilized in this study may result in unscheduled visits to the physician. If a repeat ablation procedure is indicated, it will be scheduled according to standards of clinical care.

A detailed study timeline is attached at the end of the document.

b. Study duration and visits.

We aim to complete the proposed study protocol in two years. After the ablation, patients will be followed at 3, 6 and 12 months via in clinic visit; a 1 month and 9 month follow up will take place via remote ECG transmission. Follow-up research questionnaires and post-ablation MRI will be scheduled to coincide with the routine clinical visits. Hence, no additional visits will be required of research participants unless it was not possible to schedule the MRI on the same day as clinic visits. Only then will we ask participants to present to JHH for the follow-up MRI.

c. Blinding, including justification for blinding or not blinding the trial, if applicable.

N/A

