Comparison variables will be presented as means \pm SD, and categorical variables as numbers and percentages. Differences between treatment groups will be assessed using the Pearson Chi-square test and the Wilcoxon rank-sum test. Survival curves for time to event analysis will be estimated using the Kaplan-Meier method, and the differences between the curves will be tested for significance with the log-rank statistic. Weekly event rates will be calculated by dividing the event rate by the maximum follow-up period in each arm of the Kaplan-Meier analysis. Hazard ratios will be calculated by univariate and multivariate analysis using the Cox proportional-hazards regression model. When comparing MR image characteristics as well as LA function between pre and post-ablation imaging, the Student's t-test will be using for comparison of the means. All statistical testing will be 2-tailed. Results will be considered statistically significant at a level of $p < 0.05$.

- d. Early stopping rules. N/A

8. Risks

- a. Medical risks, listing all procedures, their major and minor risks and expected frequency.

As discussed above, all procedures except the post-ablation MRI is part of the standard clinical care. In addition, groups reporting their experience with substrate-based ablation have not encountered increased complications compared to the conventional ablation procedure (Narayan et al., 2012). In addition, there is no data suggesting any health hazard associated with magnetic field exposure (Schenck, 2000). All patients with pacemakers, implanted defibrillators or electronic/metallic devices, shrapnel and other metals such as metal in the eyes will be excluded.

Gadolinium chelates used as intravenous contrast media in MRI are considered safe and do not exhibit the nephrotoxicity associated with iodinated media. The injection of contrast intravenously is not painful, but

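### The weekly event rate in section 7c divides by the longest follow-up in the arm, so it is not a rate per patient-week at risk

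*Combined protocol and SAP*

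**What the plan says.** Section 7c sets the rule for the weekly rate: "Weekly event rates will be calculated by dividing the event rate by the maximum follow-up period in each arm of the Kaplan-Meier analysis". It does not define the event rate that forms the numerator, and it does not say when follow-up time starts.

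The endpoint comes from section 7a. The analysis is time to first event: "The association of time to AF/AT recurrence with ablation strategy will be examined in 30 randomized patients". A failure counts only if it is "occurring after the 3-month blanking period following catheter ablation" and is "documented by an ECG or device recording system". Section 4a schedules follow-up to one year ("After the ablation, clinical follow-up visits are scheduled at 3, 6 and 12 months"), and the appendix timetable also ends at 12 months. Section 4a accepts gaps in monitoring: "it is not imperative that all patients complete all weekly follow up transmissions".

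No other section redefines or corrects the weekly rate. The log-rank test and the Cox hazard ratios are specified separately in section 7c and do not draw on it.

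**The concern.** In a time-to-first-event analysis a patient stops contributing time at recurrence or censoring. A weekly rate therefore needs the summed time at risk as its denominator. The arm's maximum follow-up is a single patient's time, applied to everyone. It adds weeks after failure and after loss to follow-up, and possibly the blanking weeks as well.

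Three things are at stake:

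- **Level.** The reported rates would usually be too low, and more so in arms with more recurrences.
- **Reproducibility.** With the numerator and the clock both undefined, two analysts could report different rates from the same data.
- **Later use.** Sections 1 and 11 present this study as the source of preliminary outcome data for a 300-patient trial. A weekly rate taken from it as a planning hazard would carry the error forward.

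**Working it through.** The plan gives no numeric weekly rate, so there is no figure to reproduce. The check compares the written rule with the person-time rate.

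**Inputs from the protocol**
- Blanking of 3 months (section 7a), taken as 13 weeks.
- Follow-up of 12 months (section 4a, appendix), taken as 52 weeks, so 52 − 13 = 39 weeks at risk.
- Failure of about 50%, from "Catheter ablation results in long-term AF suppression in approximately 50% of patients with persistent AF" (section 7b).
- Failure range of 20-60%, from "Based on the variable success rate of 40-80% in AF ablation" (section 7c).
- 30 patients allocated 1:1:1 (section 4a), so about 10 per arm.

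**Assumptions:** constant hazard after blanking and, unless stated otherwise, no dropout.

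**Step 1: direction.** Let an arm have n patients, d recurrences and follow-up times tᵢ. The rule with a crude numerator is (d/n)/max(t). The person-time rate is d/Σtᵢ. Because Σtᵢ ≤ n × max(t), the rule can never exceed the person-time rate.

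**Step 2: size.** With failure proportion F, the person-time rate is λ = −ln(1 − F)/39. The rule gives F/39 if time starts after blanking and F/52 if it starts at ablation.

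| F | λ per week | F/39 (ratio to λ) | F/52 (ratio to λ) |
|---|---|---|---|
| 0.20 | 0.00572 | 0.00513 (0.90) | 0.00385 (0.67) |
| 0.40 | 0.01310 | 0.01026 (0.78) | 0.00769 (0.59) |
| 0.50 | 0.01777 | 0.01282 (0.72) | 0.00962 (0.54) |
| 0.60 | 0.02349 | 0.01538 (0.65) | 0.01154 (0.49) |

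**Step 3: contrast between arms.** The shortfall grows with F, so the rule compresses differences. For 40% against 80% success, its rate ratio is 0.60/0.20 = 3.0. The hazard-based ratio is ln(0.4)/ln(0.8) = 4.1.

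**Step 4: an illustrative arm of 10.** Suppose recurrences fall 4, 10, 16, 24 and 32 weeks after blanking (86 weeks in total), and five patients are event-free to week 39 (5 × 39 = 195).
- Person-time rate: 5/(86 + 195) = 5/281 = 0.0178 per patient-week, exact Poisson 95% CI 0.0058-0.0415.
- Rule: 0.5/39 = 0.0128, or 0.5/52 = 0.0096.

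**Step 5: dependence on one patient.** Suppose one event-free patient in that arm is followed to week 60 after ablation (47 after blanking).
- The rule's result falls by 1 − 39/47 = 17%, or by 1 − 52/60 = 13%.
- The person-time rate becomes 5/289 = 0.0173, a fall of 3%. With a 12-month cap it does not change.

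**Step 6: dropout (assumed 0-30%) at the same true hazard.** With a crude numerator and a 39-week divisor, the rule drifts from 0.0128 to 0.0110. The patient-week rate stays at 0.0178.

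**Step 7: a Kaplan-Meier numerator.** Without censoring this equals the crude proportion, so Step 1 applies. With censoring the direction can reverse. In simulated arms of 10 with assumed dropout of 0/10/20/40% and the clock starting after blanking, the rule exceeded the person-time rate in 0/1/2/5% of arms at 50% failure and 0/8/12/22% at 20% failure. The last figure is about 18% if arms with no recurrence are kept in the base. With the clock at ablation it was at most 3%. The crude version never exceeded the person-time rate.

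**The case against.** The strongest reply is that the plan never promises a person-time rate. Its sentence refers to the Kaplan-Meier analysis. If the numerator is the Kaplan-Meier cumulative incidence, the result is an average weekly cumulative incidence, which can be interpreted. On that reading the fault is a loose label. This stands in part: the quantity would have a meaning, but it would still not be a rate per week at risk, and the plan does not say this reading is intended. With a crude numerator the objection fails.

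Other points limit the consequence, and they stand:

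- The weekly rate feeds no test, sample size calculation or stopping rule.
- The larger shortfalls (0.67-0.49) require the clock to start at ablation; a clock starting after blanking is equally open.
- The common 12-month schedule should usually keep the maxima similar between arms, so the week-60 example shows fragility and is not a forecast.
- With about 10 patients per arm, both results of the rule lie inside the person-time interval in the worked arm. The discrepancy is one of definition, however, and a wide interval does not correct it.

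Finally, the proposed sentence sets a censoring rule, a 12-month cap and an interval method, which goes beyond the bare defect. A person-time rate does need a defined start and end. The cap and the Poisson interval are reasonable choices rather than corrections of an error.

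**Conclusion.** The concern holds. Followed as written, section 7c would not yield rates per patient-week at risk. With a crude numerator, or a Kaplan-Meier numerator without censoring, the result cannot exceed the true rate. At the protocol's own 50% figure it is 28% low (39-week divisor) or 46% low (52-week divisor). With a Kaplan-Meier numerator and censoring it can occasionally be too high. These sizes rest on a constant hazard, complete follow-up and months converted to 13 and 52 weeks; the inequality in Step 1 needs none of these. The damage is confined to one descriptive output, but the sentence should be changed.

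**What to change.** Replace the sentence in section 7c with:

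> Weekly event rates will be the number of patients with a first AF/flutter/AT recurrence after blanking divided by total patient-weeks at risk, counted from the end of the 3-month blanking period to first recurrence, last rhythm assessment of any type (device transmission or visit ECG) or 12 months, whichever is first, with exact Poisson 95% CIs.

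Report 12-month Kaplan-Meier freedom from AF/AT alongside. Ending time at the last rhythm assessment follows from the endpoint, which needs a recorded tracing, and from the tolerance of missed transmissions. The Poisson interval assumes a constant rate, which should be stated.

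A smaller alternative is to drop the weekly rate and report Kaplan-Meier estimates at fixed times.

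The cost is one sentence and minor analysis work, with no new data. The one downside is that the reported weekly rates will usually be higher than under the current rule.
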